Appendix 2: Survey Questionnaire

This questionnaire asks about your general health with a focus on your migraine, your health during and after your "study pregnancy", and about your child's health.

Please refer to your latest, completed, pregnancy (if you are currently pregnant, please do not refer to the current pregnancy when answering the following questions). We will refer to the latest, completed, pregnancy as the "study pregnancy".

It will take approximately 30-40 minutes to complete the questionnaire.

Part 1 – Demographics and medical history prior to "study pregnancy"

1. What is your date of birth?

Mark on Calendar

- 2. Are you of Hispanic, Latino, or of Spanish origin?
 - Yes
 - No
- 3. How would you describe yourself?
 - American Indian or Alaska Native
 - Asian
 - Black or African American
 - Hispanic or Latino
 - Native Hawaiian or Other Pacific Islander
 - White or Caucasian
 - Other
- 4. What is your height (feet, inches)

Choose: Pull down menu between 4.0 to 7.0 with 0.1 jumps. Allow other.

5. Weight (lb) at the beginning of your study pregnancy

Choose: Pull down menu between 85 and 300 lb, with jumps of 5 units. Allow other.

6. Do you have a history of any of the following medical conditions, that was diagnosed prior to your study pregnancy? Check all that apply

QMS document

TCH-011 Clinical Study Protocol

Doc ID: TECXXXX
Revision #: 1.0

Page: 13 of 25

AIDS/	/HIV
-------------------------	------

- Anemia
- Asthma
- Autoimmune disease (such as lupus, rheumatoid arthritis etc)
- Clinically diagnosed depression or any other psychiatric diseases
- Clinical obesity (body mass index, BMI, greater than 30)
- Endometriosis
- Epilepsy
- Kidney disease
- High blood pressure
- Pre-pregnancy diabetes
- Polycystic ovary syndrome (PCOS)
- Sexually transmitted disorders
- Thyroid disease
- Other diseases
 - Please specify _____

Check all that applies

- 7. Prior to your "study pregnancy", do you have a history of (Check all that applies)
 - Smoking
 - Excessive alcohol consumption (more than 1 glass of wine/day or any other alcohol equivalent)
 - Using medical marijuana
 - Using recreational drugs

Multiple choice

- 8. On average, how many days per month did you experience migraine in the 6 months prior to the "study pregnancy"?
 - Less than 4 days per month
 - 4-8 days per a month

QMS document

TCH-011 Clinical Study Protocol

Doc ID: TECXXXX

Revision #: 1.0

Page: 14 of 25

- 9-14 days per month
- 15 days or more per month

Multiple choice

- 9. How often did you use acute treatments for migraine (either pharmaceutical drugs and/or devices) in the six months prior to the "study pregnancy"?
 - Less than 4 times per month
 - 4-8 times per a month
 - 9-14 times per month
 - 15 times or more per month

Multiple choice

- 10. Please read carefully and mark all types of ACUTE treatments (either pharmaceutical drugs and/or devices) you used for migraine in the six months prior to the study pregnancy. Please include any treatment, even if used only once. In cases where two names are used, one is the generic name and one is the branded name (Check all that applies)
 - Tylenol®, or any other acetaminophen/paracetamol
 - Excedrin® (Aspirin and paracetamol and caffeine) -
 - Advil®, Motrin®, or any other ibuprofen
 - Aleve®, Anaprox®, or any other Naproxen sodium
 - Other over-the-counter medications
 - Cambia[®] (Diclofenac)
 - Cafergot®, Ergomar® (Ergotamines)
 - Tivorbex® (Indomethacin)
 - Imitrex® (sumatriptan)
 - Maxalt[®] (rizatriptan)
 - Relpax® (Eletriptan)
 - Treximet[®] (sumatriptan/naproxen sodium)
 - Axert (Almotriptan), Zomig[®] (zolmitriptan)
 - Other Oral Triptan

QMS document

TCH-011 Clinical Study Protocol

Doc ID: TECXXXX

Revision #: 1.0

Page: 15 of 25

- Nurtec® ODT (Rimegepant)
- Ubrelvy® (Ubrogepant)
- Tosymra® (sumatriptan nasal spray)
- Onzetra Xsail[®] (sumatriptan nasal poder)
- Zembrace SymTouch® (sumatriptan injection)
- Zomig[®] nasal spray (Zolmitriptan)
- Migranal[®] (Dihydroergotamine Mesylate Spray)
- Trudhesa[™] (dihydroergotamine mesylate nasal spray)
- Other nasal / injectable medication
- Reyvow (Lasmiditan®)
- Nerivio® (Remote Electrical Neuromodulation)
- Other devices (e.g., gammaCore[™], Cefaly[®], Relivion[®])
- Zofran® (Ondansetron)
- Reglan® (Metoclopramide)
- Compazine® (Prochlorperazine)
- Phenergan® (Promethazine)
- Other medication for nausea/vomiting
- Other medications
- None

Check all that applies

- 11. Please mark the PREVENTIVE migraine treatment (either pharmaceutical drugs and/or devices) you used during the six months prior to the study pregnancy. (Check all that applies)
 - Amitriptyline, or any other generic tricyclic antidepressants
 - Inderal[®] (Propranolol)
 - Topiramate® (Topamax)
 - Other generic oral preventive medication
 - Nortriptyline (Pamelor), or any othernon-generic tricyclic antidepressants

QMS document

TCH-011 Clinical Study Protocol

Doc ID: TECXXXX
Revision #: 1.0

Page: 16 of 25

PIO	locoi	

- Botox® injection for migraine prevention (Botulinum toxin)
- Aimovig[®] (Erenumab)
- Ajovy® (Fremanezumab)
- Emgality® (galcanezumab-gnlm)
- Vyepti® (eptinezumab-jjmr)
- Nurtec® ODT (Rimegepant)
- Devices (e.g., gammaCore, Cefaly)
- Other
- Did not use any preventive treatment

Check all that applies

- 12. Have you been diagnosed with migraine with aura by a licensed healthcare provider? (Aura is a neurologic symptom that occurs typically before or during migraine that lasts 5-60 minutes and is characterized by an evolution of neurologic symptoms such as flashing lights or colors that grow in your visual field)
 - Yes
 - No
- 13. Do you usually experience aura right before your headache attacks?
 - Always
 - Sometimes
 - Never
- 14. Have you ever used Nerivio® to treat your migraine attacks?
 - Yes
 - No
- 15. How many prior pregnancies before the "study pregnancy" have you had?

Choose from 0 to 10 and "more than 10"

16. How many of these were completed pregnancies?

QMS document

TCH-011 Clinical Study Protocol

Doc ID: TECXXXX

Revision #: 1.0

Page: 17 of 25

Show question if >0 in the previous question. Responses: Choose from 0 to 10 and "more than 10"

- 17. Is there a family history of congenital defects or malformations?
 - Yes
 - No

Part 2 – Study pregnancy

The following questions refer to you latest, completed, pregnancy, termed "study pregnancy" (if you are currently pregnant, please do not refer to this pregnancy when answering the questionnaire).

- 18. What was the first day of the last menstrual period (LMP) before your "study pregnancy"? (Please provide accurate month and year. If you do not recall the exact day within the month, please choose 1st day of the month).
 - Choose on calendar / enter date (month, year; day is optional)

Year and month are good enough. Day is optional.

- 19. What was the delivery date of your "study pregnancy"?
 - Choose on calendar
- 20. What was your baby's gestational age at delivery or at the end of pregnancy (pregnancy length measured by number of weeks and days) of your "study pregnancy"

Choose on "roller", allow weeks (6 to 42 weeks) and days (+0 to 6 days). If possible, allow weeks and days separately..

- 21. What is the status of your "study pregnancy"?
 - Live birth
 - Elective termination
 - Spontaneous abortion (or miscarriage)
 - Late fetal death
- 22. If you had a miscarriage, what was its cause?
 - I did not experience a miscarriage
 - Abnormal fetal development

QMS document

TCH-011 Clinical Study Protocol

Doc ID: TECXXXX

Revision #: 1.0 Page: 18 of 25

- Abnormal placenta (such as abruption)
- Blood disorders such as thrombophilias
- Cervical insufficiency
- Chromosomal abnormalities
- Maternal anatomic abnormalities such as uterine fibroids, polyps or adhesions in uterus
- Physical trauma
- Unknown cause
- Other

23. Delivery circumstances (Check all that applies)

- Spontaneous labor
- Induction of labor
- Past due date
- Decreased fetal movement
- Cardiac arrhythmia in fetus
- Pregnancy induced hypertension such as gestational hypertension or pre-eclampsia
- HELLP syndrome
- Premature rupture of membranes
- Other complications or medical concerns

Check all that apply

24. What was the mode of delivery?

- Repeat Cesarean Delivery
- Primary Cesarean delivery
- Spontaneous vaginal delivery

25. During your "study pregnancy", did you do any of the following (select all that apply)

Smoking

QMS document

TCH-011 Clinical Study Protocol

Doc ID: TECXXXX Revision #: 1.0

Page: 19 of 25

•	Excessively consuming alcohol (more than 1 glass of wine/day or any other
	equivalent)

- Using recreational drugs

Using medical marijuana

Check all that apply

26. Was the baby discharged from the hospital at the same time with yo	u?
--	----

- Yes
- No
- 27. Did you use Nerivio to treat your migraine attacks during your "study pregnancy"?
 - Yes
 - No
- 28. During your "study pregnancy", did you use Nerivio for migraine treatment at least 3 times?
 - Yes
 - No

Part 3 – Migraine during the study pregnancy

The following questions refer to your latest, completed, pregnancy referred to as the "study pregnancy" (if you are currently pregnant, please do not refer to this pregnancy when answering the questionnaire).

- 29. How many migraine days per month (on average) did you have during the FIRST trimester of your "study pregnancy"?
 - Less than 4 days per month
 - 4-8 days per a month
 - 9-14 days per month
 - 15 days or more per month

Multiple choice

30. How often did you use ACUTE treatments for migraine during the FIRST trimester of your "study pregnancy"?

QMS document

TCH-011 Clinical Study Protocol

Doc ID: TECXXXX

Revision #: 1.0

Page: 20 of 25

- Less than 4 times per month
- 4-8 times per a month
- 9-14 times per month
- 15 times or more per month

Multiple choice

- 31. How many migraine days per month (on average) did you have during the SECOND trimester of your "study pregnancy"?
 - Less than 4 days per month
 - 4-8 days per a month
 - 9-14 days per month
 - 15 days or more per month

Multiple choice

- 32. How often did you use ACUTE treatments for migraine during the SECOND trimester of your "study pregnancy"?
 - Less than 4 times per month
 - 4-8 times per a month
 - 9-14 times per month
 - 15 times or more per month

Multiple choice

- 33. How many migraine days per month (on average) did you have during the THIRD trimester of your "study pregnancy"?
 - Less than 4 days per month
 - 4-8 days per a month
 - 9-14 days per month
 - 15 days or more per month

Multiple choice

- 34. How often did you use ACUTE treatments for migraine during the THIRD trimester of your "study pregnancy"?
 - Less than 4 times per month

QMS document

TCH-011 Clinical Study Protocol

Doc ID: TECXXXX

Revision #: 1.0

Page: 21 of 25

- 4-8 times per a month
- 9-14 times per month
- 15 times or more per month

Multiple choice

35. Please mark all types of ACUTE treatments (either pharmaceutical drugs and/or devices) you used for migraine during the "study pregnancy". Please include any treatment, even if used only once.

For each treatment type used, please indicate if you felt SAFE using it during the pregnancy by choosing the matching option of the dropdown menu.

• Tylenol[®], or any other acetaminophen/paracetamol

Did you feel safe using this medication during the pregnancy?

- Yes
- No
- Excedrin® (Aspirin and paracetamol and caffeine) -
- Advil®, Motrin®, or any other ibuprofen
- Aleve[®], Anaprox[®], or any other Naproxen sodium
- Other over-the-counter medications
- Cambia[®] (Diclofenac)
- Cafergot[®], Ergomar[®] (Ergotamines)
- Tivorbex® (Indomethacin)
- Imitrex® (sumatriptan), Maxalt® (rizatriptan), Relpax® (Eletriptan), Treximet® (sumatriptan/naproxen sodium), Axert (Almotriptan), Zomig® (zolmitriptan), or any other Oral Triptan
- Nurtec® ODT (Rimegepant)
- Ubrelvy® (Ubrogepant)
- Tosymra® (sumatriptan nasal spray), Onzetra Xsail® (sumatriptan nasal poder),
 Zembrace SymTouch® (sumatriptan injection); Zomig® nasal spray (Zolmitriptan),
 Migranal® (Dihydroergotamine Mesylate Spray); Trudhesa™ (dihydroergotamine
 mesylate nasal spray), or any other nasal / injectable medication
- Reyvow (Lasmiditan®)
- Nerivio® (Remote Electrical Neuromodulation)

QMS document

TCH-011 Clinical Study Protocol

Doc ID: TECXXXX

Revision #: 1.0

Page: 22 of 25

- Other devices (e.g., gammaCore[™], Cefaly[®], Relivion[®])
- Zofran® (Ondansetron), Reglan® (Metoclopramide), Compazine® (Prochlorperazine),
 Phenergan® (Promethazine), or any other medication for nausea/vomiting
- Other medications
- None

Check all that applies

36. Rate your overall satisfaction with your acute migraine treatment during your "study pregnancy", when 1 = Highly dissatisfied, 10 = Highly satisfied

Drop Down menu, with options 1-to-10 AND Not relevant (I did not use acute migraine treatment during my pregnancy)

37. Please mark all types of PREVENTIVE treatments (either pharmaceutical drugs and/or devices) you used for migraine during the "study pregnancy". Please include any treatment, even if used only once.

For each treatment type used, please indicate if you felt safe using it during the pregnancy by choosing the matching option of the dropdown menu.

- Amitriptyline, or any other generic tricyclic antidepressants
- Inderal[®] (Propranolol)
- Topiramate® (Topamax)
- Other generic oral preventive medication
- Nortriptyline (Pamelor), or any othernon-generic tricyclic antidepressants
- Botox® injection for migraine prevention (Botulinum toxin)Aimovig® (Erenumab),
 Ajovy® (Fremanezumab), Emgality® (galcanezumab-gnlm), Vyepti® (eptinezumabjjmr), that is any CGRP monoclonal antibodies (CGRP mAbs)
- Nurtec® ODT (Rimegepant)
- Devices (e.g., gammaCore, Cefaly)
- Other
- Did not use any preventive treatment
- 38. Rate your overall satisfaction with your PREVENTIVE migraine treatment during your "study pregnancy", when 1 = Highly dissatisfied, 10 = Highly satisfied

Drop Down menu, with options 1-to-10 AND Not relevant (I did not use preventive migraine treatment during my pregnancy)

TCH-011 Clinical Study Protocol

Doc ID: TECXXXX
Revision #: 1.0

Page: 23 of 25

- 39. Were you admitted to the emergency room (ER) or hospital for management/evaluation of headache during your "study pregnancy"?
 - Yes
 - No

Part 4 - Migraine postpartum

- 40. How many migraine days per month (on average) did you have in the 3 months postpartum after your "study pregnancy"?
 - Less than 4 days per month
 - 4-8 days per a month
 - 9-14 days per month
 - 15 days or more per month
- 41. Did you breast-feed during the first 3 months postpartum following your "study pregnancy"?
 - Yes
 - No

Part 5 – Baby's health

- 42. For your "study pregnancy", what is your baby's sex at birth?
 - Male
 - Female
- 43. What was the baby's birth weight (lbs)?

Choose on a drop-down menu, including the following answers:

- Less than 1.5 kg / 3.4 pounds
- Between 1.5 and 2.49 kg / between 3 pounds 4 ounces and 5 pounds 8 ounces
- Weights with jumps of 100 gram up to 4 kg and the equivalent in pounds (2.5, 2.6, 2.7, 4)
- More than 4 kg / 8 pounds and 13 ounces

QMS document

TCH-011 Clinical Study Protocol

Doc ID: TECXXXX
Revision #: 1.0

Page: 24 of 25

44.	Was	the	baby	diagnosed	with	any	birth	defects?
-----	-----	-----	------	-----------	------	-----	-------	----------

- No
- Yes
- 45. Were there any complications with the baby after delivery?
 - No
 - Yes

If Yes, what type of complication?

- Neonatal jaundice,
- Newborn required admission to the neonatal intensive care unit
- Respiratory distress syndrome
- Infection such as sepsis
- Failure to thrive
- Low birth weight
- Other
- 46. Did your baby meet routine developmental milestones at 3 months? of life (such as smiling, gurgle, visually tracking objects, and rolling over within the first 3 months)
 - No
 - Yes
- 47. What was your baby's APGAR scores at 1 minute after birth?

We know it might be difficult to remember this score. Please check your discharge notes to find the 1 minute APGAR score, although not all notes include this information:

- Choose 1-10
- Don't know / Can't find the 5 min APGAR score

Use a dropdown menu, and add the option can't find

48. What was your baby's APGAR scores 5 minutes after birth? We know it might be difficult to remember this score. Please check your discharge notes to find the 5 minutes APGAR score, although not all notes include this information:

QMS document

TCH-011 Clinical Study Protocol

Doc ID: TECXXXX

Revision #: 1.0

Page: 25 of 25

- Choose 1-10
- Don't know / Can't find the 5 min APGAR score

Use a dropdown menu, and add the option can't find

- 49. Does the baby have any additional APGAR scores at 10, 15 or 20 minutes?
 - Yes
 - No
 - Don't know

If Yes, go to the next page, and ask for APGAR scores at 3 additional time points. Otherwise (answer: No or Don't know), go directly to the last page.

Page break

- 50. What was your baby's APGAR scores 10 minutes after birth? We know it might be difficult to remember this score. Please check your discharge notes to find the 5 minutes APGAR score:
 - Choose 1-10
 - Don't know / Can't find the 5 min APGAR score
- 51. What was your baby's APGAR scores 15 minutes after birth? We know it might be difficult to remember this score. Please check your discharge notes to find the 5 minutes APGAR score:
 - Choose 1-10
 - Don't know / Can't find the 5 min APGAR score
- 52. What was your baby's APGAR scores 20 minutes after birth? We know it might be difficult to remember this score. Please check your discharge notes to find the 5 minutes APGAR score:
 - Choose 1-10
 - Don't know / Can't find the 5 min APGAR score

Page break

Thank you for your participation in this study. The payment will be sent to your email following the verification of your participation with the clinic (approximately 48 hours). Please contact [contact] if you did not receive the payment within this time.

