- 6. Meeting developmental milestones following 3 months postnatal (% of babies)
- 7. Visits to the emergency room or urgent care due to pregnancy and/or migraine symptoms during pregnancy and 3 months postpartum period (# of events)

Exploratory endpoints: Difference between the study group and the control group in:

- 1. Overall subjective **feeling of safety** using acute migraine treatments during pregnancy (in subjects who used such treatments).
- 2. Overall subjective **satisfaction** with the acute migraine therapies used during the pregnancy (in subjects who used such treatments).
- 3. APGAR score at 5 minutes.

Data analysis

Statistical Hypothesis

The goal of the proposed study is to test the null hypothesis that treating with Nerivio during pregnancy does not impose a safety risk relative to standard care migraine treatment for pregnant women. In other words, the hypothesis is that the means of the two populations are equal. Thus, in this study, the following hypotheses will be tested:

• Null hypothesis: H0: GAt = GAc

• Alternate hypothesis: H1: GAt ≠ GAc

Where GAt and GAc are the average Gestational Age in the study group and control group, respectively. If the null hypothesis is not rejected, the study will be deemed successful. The criterion for significance has been set at 0.05. The test is 2-tailed.

TCH-011 Clinical Study Protocol

Doc ID: TECXXXX

Revision #: 1.0

Page: 7 of 25

Planned Sample Size

Based on USA data from 2020 [Osterman M, et al. Births: Final Data for 2020. Natl Vital Stat Rep. 2021] we assume mean gestational age (GA) of 38.4 with standard deviation of 2.7 (range 26-42).

With the proposed sample size of 114 for each group, the study will have power of 80% to yield a statistically significant result. This computation assumes that the mean difference is less than 1.0 week, and the common within-group standard deviation is 2.7. This effect was selected as the smallest effect that would be important to detect.

Precision for estimating the effect size: We further estimate the mean difference between the two populations. On average, a study of this design would enable us to report the mean difference with a precision (95% confidence level) of plus/minus 0.70 weeks.

Given this statistical requirement up to 400 participants will be recruited per group.

Statistical Analysis Plan

Data will be collected from all patients recruited to the study. Data analysis will not include patients who are:

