- Obese (BMI>=40) at the beginning of the study pregnancy
- Did not have their last menstrual period (LMP) between November 1st, 2019 March 31st, 2021
- In the study group, did not use Nerivio for at least 3 treatments (≥30 minutes/treatment) during the "study pregnancy"
- In the control group, did use Nerivio before, during, or in the 3 months following the "study pregnancy"

TCH-011 Clinical Study Protocol

Doc ID: TECXXXX

Revision #: 1.0

Page: 8 of 25

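### The survey's height menu in 0.1 steps does not fit its feet-and-inches label, so the BMI>=40 analysis exclusion can be misapplied to women near the cut-off

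*Combined protocol and SAP*

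**What the plan says.** Question 4 of the survey (Appendix 2, Part 1) begins "What is your height (feet, inches". Its answer format is a "Pull down menu between 4.0 to 7.0 with 0.1 jumps", followed by permission to enter another value. Question 5 asks for "Weight (lb) at the beginning of your study pregnancy", with the format "Pull down menu between 85 and 300 lb, with jumps of 5 units. Allow other".

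The Statistical Analysis Plan states "Data analysis will not include patients who are" in any of several listed categories. The first is "Obese (BMI>=40) at the beginning of the study pregnancy". The plan gives no formula for BMI and no rule for turning a menu value such as 5.5 into inches.

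No other item can supply the exclusion. The screening questionnaire in Appendix 1 asks for neither BMI, height nor weight. The one other BMI item is a tick box in question 6, "Clinical obesity (body mass index, BMI, greater than 30", which uses a different cut-off.

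**The concern.** Height in feet and inches has twelve steps per foot, and the menu has ten. Each way of reading the menu therefore has a fault. Under the printed label, 5.9 is followed directly by 6.0, and 10 and 11 inches are absent. As decimal feet, the scale is complete but is not what the label asks for. Different women may answer in different ways, and the stored number does not show which way was meant.

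The field feeds a rule that decides who is analysed. A height taken too tall lowers BMI and can keep a woman whom the plan excludes. A height taken too short raises BMI and can remove a woman whom the plan includes. Neither error would be visible in the data afterwards.

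**Working it through.** The documents state no figure that depends on the height item, so there is none to reproduce first.

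**Inputs.** Height label and menu: Appendix 2, question 4. Weight in pounds: Appendix 2, question 5. Cut-off of 40: Statistical Analysis Plan. The formula is the ordinary unit conversion, which the plan does not state: BMI = 703.07 × lb / in².

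**Step 1: what the menu can hold.** From 4.0 to 7.0 in steps of 0.1 there are 31 values.
- *Feet.inches:* the missing heights are 4 ft 10 in, 4 ft 11 in, 5 ft 10 in and 5 ft 11 in (also 6 ft 10 in and 6 ft 11 in).
- *Decimal feet:* 70/12 = 5.83, which rounds to 5.8 (69.6 in). 71/12 = 5.92, which rounds to 5.9 (70.8 in). Every height fits to within half a step, 0.05 × 12 = 0.6 in.

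So the missing heights arise under one reading only.

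**Step 2: how far the readings differ.** An entry f.i means 12f + i inches under the label and 12f + 1.2i inches as decimal feet. The gap is 0.2i inches, from 0.2 in at x.1 to 1.8 in at x.9. The weight at which BMI reaches 40 is 40 × in² / 703.07.

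| Entry | Feet.inches | Decimal feet | BMI lower if decimal | BMI 40 at, feet.inches | BMI 40 at, decimal | Band |
|---|---|---|---|---|---|---|
| 5.1 | 61 in | 61.2 in | 0.7% | 211.7 lb | 213.1 lb | 1.4 lb |
| 5.5 | 65 in | 66.0 in | 3.0% | 240.4 lb | 247.8 lb | 7.4 lb |
| 5.9 | 69 in | 70.8 in | 5.0% | 270.9 lb | 285.2 lb | 14.3 lb |

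Only a weight inside the band changes a woman's status. On the 5 lb weight menu that is one value at 5.5 (245 lb) and three at 5.9 (275, 280 and 285 lb).

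**Step 3: errors in both directions.**
- *Wrongly kept.* 5.9 is meant as 5 ft 9 in and read as decimal feet. (70.8/69)² = 1.053 and 40 × 1.053 = 42.1, so true BMI from 40.0 to about 42.1 is kept. At 280 lb, true BMI is 703.07 × 280 / 69² = 41.3, and the scored value is 703.07 × 280 / 70.8² = 39.3.
- *Wrongly removed.* A woman of 5 ft 6 in enters 5.5 as decimal feet, and it is read as 5 ft 5 in. At 245 lb, true BMI is 703.07 × 245 / 66² = 39.5, and the scored value is 703.07 × 245 / 65² = 40.8.
- *Wrongly removed, missing height.* A woman of 5 ft 10 in picks 5.9, and it is read as 5 ft 9 in. At 275 lb, true BMI is 703.07 × 275 / 70² = 39.5, and the scored value is 703.07 × 275 / 69² = 40.6.

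**Step 4: the extreme case, under an assumption.** Suppose 5.10 is typed as a free entry, stored as the number 5.1 and read as 61 in. Then (70/61)² = 1.317, a 32% inflation. Any true BMI from 40/1.317 = 30.4 (about 212 lb) upward would score 40 or more. At 215 lb, 30.8 becomes 40.6.

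**The case against.** The full answer format is "Pull down menu between 4.0 to 7.0 with 0.1 jumps. Allow other". A woman of 5 ft 10 in who finds no entry for her height can type it, and she is the respondent most likely to look for another option. The question can therefore hold the value; only the menu lacks it. The label also names its units. Both points stand. A reader might infer that these heights cannot be recorded at all or that no unit is stated, and the documents support neither.

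The missing heights and the decimal misreading belong to different readings of the menu, so one respondent's entry should not be charged with both. That is right, but the plan does not settle which reading applies.

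The 32% error does not follow from the menu, which has no 5.10. It needs a free entry stored as a number, and the documents do not say how free entries are stored. It should be treated as a possibility only.

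A reader might also infer that a BMI covariate would be corrupted. The Statistical Analysis Plan names no covariates and no adjusted model, and BMI appears there only as an exclusion. Nor do the documents show bias between the groups. Form and exclusion are the same in both, and no effect on gestational age at delivery is shown.

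Finally, weight is itself coarse. A 5 lb step rounds by up to 2.5 lb, about 1% at 240 lb. That puts the height error in proportion, but at 5.5 and above the height ambiguity is three to five times larger. Unlike rounding, it can be avoided altogether.

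**Conclusion.** The point holds as a minor defect of the form that reaches a stated analysis rule. The 0.1 steps do not fit the feet-and-inches label, and no conversion is given. BMI at the cut-off can be derived only from questions 4 and 5. The plan does not say that it will be derived in this way, but it offers no other route.

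The realistic size is a BMI difference of up to about 5% for entries from 5.1 to 5.9. It matters only for weights within a band of about 7 lb at 5.5 and 14 lb at 5.9. The 32% case rests on the storage assumption above.

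The documents give no distribution of height or weight, so the number of women misclassified cannot be computed. It is probably small, because the bands are narrow. Sample size is not at issue: 114 per group are required, and up to 400 per group may be recruited.

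**What to change.** Replace question 4 with two menus, feet (4 to 7) and inches (0 to 11), stored as separate integers. State in the Statistical Analysis Plan that BMI is computed from total inches and pounds, and give the formula. Every height is then recordable without free entry, and BMI 40 falls at one weight per height: 240.4 lb at 5 ft 5 in, 270.9 lb at 5 ft 9 in, 278.8 lb at 5 ft 10 in and 286.8 lb at 5 ft 11 in. The form already takes this approach for gestational age, where question 20 prefers that the two units be captured separately.

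The cost is one field change and one sentence in the plan before launch, with no change to the sample size. If responses have already been collected, an ambiguous entry cannot be resolved from the stored value. In that case, apply the exclusion under both readings, report how many women change status, and give the primary comparison both ways.
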